4. PARTICIPANT SELECTION AND WITHDRAWAL CRITERIA

4.1. SELECTION OF STUDY PARTICIPANTS

Approximately 210 patients with genetically confirmed FSHD1 and 20 patients with genetically confirmed FSHD2 will be enrolled at approximately 36 sites in North America and Europe. Eligibility will be reviewed and documented by an appropriately qualified member of the Investigator's team before patients are enrolled. Patients will be assigned to study treatment only if they meet all the inclusion criteria and none of the exclusion criteria.

Deviations from the inclusion and exclusion criteria are not allowed because they can potentially jeopardize the scientific integrity of the study, regulatory acceptability, or patient safety. Therefore, adherence to the eligibility criteria as specified in the protocol is essential.

4.1.1. Part A: Placebo-Controlled Treatment Period

4.1.1.1. Inclusion Criteria

1. Patient will sign and date an informed consent form (ICF).
2. Patients will have a diagnosis of FSHD1 or FSHD2 verified by genetic testing (see [Section 6.2.1](#)).
 - Randomization will be stratified for FSHD1 to ensure that treatment allocation is balanced across FSHD repeat number categories (ie, 1 to 3 repeats versus 4 to 9 repeats).
 - Randomization will be stratified for FSHD2 to ensure that an equal number of patients will be allocated to treatment and placebo.
3. Patients will have a Clinical Severity Score of 2 to 4 (Ricci score; range 0 to 5) at screening. Patients who are wheelchair-dependent or dependent on walker or wheelchair for activities are not permitted to enroll in the study.
4. Patients with screening total RSA (Q1-Q4) without weight in the dominant UE assessed by RWS ≥ 0.2 and ≤ 0.7 .
5. Willing and able to comply with scheduled visits, treatment plan, study restrictions, laboratory tests, contraceptive guidelines, and other study procedures.
6. No contraindications to MRI.
7. Patients (male and female) will be between the ages of 18 and 65 years at the time of consent, inclusive.
 - A female patient is eligible to participate if she is of non-childbearing potential, defined as pre-menopausal females with a documented hysterectomy, bilateral salpingectomy, or bilateral oophorectomy; if she is postmenopausal, defined as no menses for 12 months without an alternative medical cause; OR

- If of child-bearing potential, she is using a highly effective method for avoidance of pregnancy for the duration of dosing and until 90 days after the last dose. For details regarding contraception requirements, refer to [Section 5.5.1.1](#).
- Male patients must agree to use one of the contraception methods listed in [Section 5.5.1](#). This criterion must be followed from the time of the first dose of study medication and until 90 days after the last dose of study drug.

4.1.1.2. Exclusion Criteria

1. History of any illness or any clinical condition that, in the opinion of the Investigator, might confound the results of the study or pose an additional risk in administering study drug to the patient. This may include, but is not limited to, history of relevant drug or food allergies; history of cardiovascular or central nervous system disease; history or presence of clinically significant pathology; clinically significant history of mental disease.
2. Previously diagnosed cancer that has not been in complete remission for at least 5 years. Localized carcinomas of the skin and carcinoma in situ of the cervix that have been resected or ablated for cure are not exclusionary.
3. For patients who are on drug(s) or supplements that may affect muscle function, as determined by the Investigator, or that are included in the list of drugs presented in [Appendix 3](#): patients must be on a stable dose of that drug(s) or supplement for at least 3 months prior to the first dose of study drug and remain on that stable dose for the duration of the study. Changes to the dose or treatment discontinuation during the study can only be done for strict medical reasons by the treating physician with clear documentation and notification to the Sponsor.
4. History of febrile illness within 5 days before the first study drug dose. Patients who were healthy during screening but develop febrile illness in the 5 days before randomization need to have the baseline visit postponed until the febrile illness is fully resolved (fever-free without the use of antipyretic agents for 24 hours). Once the febrile illness is fully resolved, the patient's baseline visit can be scheduled. The duration of the screening period in such cases can be extended to up to 35 days.
5. Known active opportunistic or life-threatening infections including HIV and hepatitis B or C.
6. Known active or inactive tuberculosis infection.
7. Current acute liver disease or chronic liver disease as defined by any of the following:
 - Current ALT $\geq 2 \times$ upper limit of normal (ULN) or total bilirubin $> 1.5 \times$ ULN (unless participant has Gilbert's syndrome characterized by the combination of total bilirubin $< 3 \times$ ULN, direct bilirubin within the normal range and normal ALT and AST, or the presence of mutations in the UDP-glucuronosyltransferase 1 gene, indicative of Gilbert's syndrome).
 - Positive for hepatitis B surface antigen.

- Positive for hepatitis C antibody unless additional testing for hepatitis C viral RNA is negative, ALT is $< 2 \times$ ULN and total bilirubin is $\leq 1.5 \times$ ULN, indicating inactive/resolved hepatitis C infection.

8. Known severe renal impairment (defined as a glomerular filtration rate of < 30 mL/min/1.73 m²).
9. Standard 12-lead ECG demonstrating QTcF >450 msec for male patients and QTcF >470 msec for female patients at screening. If QTcF exceeds 450 msec for males or 470 msec for females, the ECG will be repeated 2 more times, and the average of the 3 QTcF values will be used to determine the patient's eligibility.
10. History of cardiac dysrhythmias requiring anti-arrhythmia treatment(s); or history or evidence of abnormal ECGs that, in the opinion of the Investigator or Medical Monitor, would preclude the patient's participation in the study.
11. Male patients with a female partner who is planning to become pregnant during the study or within 90 days after the last study drug dose.
12. Concomitant use of cytotoxic chemotherapy for cancer or known ongoing or anticipated use of chronic severe immunosuppressive agents.
13. Positive pregnancy test, known to be pregnant or lactating, or planning to become pregnant during study drug administration and until 90 days after last dose.
14. Any current mental condition (psychiatric disorder, senility or dementia) that may affect study compliance or prevent understanding of the aims, investigational procedures, or possible consequences of the study.
15. Patient has any condition possibly affecting drug absorption (eg, gastrectomy, cholecystectomy, or other gastrointestinal tract surgery, except appendectomy).
16. History of alcohol, analgesic/opioid, and/or illicit drug abuse, as defined by the Diagnostic and Statistical Manual of Mental Disorders, Fifth Edition (American Psychiatric Association, 2013), in the last 6 months before screening or a positive test for drugs of abuse at screening. Use of CBD/THC is permitted.
17. Use of another investigational product within 30 days or 5 half-lives (whichever is longer) or according to local regulations, or currently participating in a study of an investigational device.
18. Current or anticipated participation in a natural history study. Previous participation is allowed but patients cannot continue after enrollment in Study 1821-FSH-301.
19. Known hypersensitivity or intolerance to losmapimod or any of its excipients.
20. Previous participation in a Fulcrum-sponsored FSHD losmapimod study (FIS-001-2019 or FIS-002-2019).
21. Anticipated inability to comply with any study procedures, including participation in study visits according to the visit schedule through 48 weeks.
22. Abnormal laboratory results indicative of any significant medical disease that, in the opinion of the Investigator, would preclude the patient's participation in the study.

23. Patient, or close relative of the patient, is the Investigator or a subinvestigator, research assistant, pharmacist, study coordinator, or other staff directly involved with the conduct of the study at that site.
24. Patient is vulnerable (i.e., deprived of freedom), including inmates of psychiatric wards and prison or state institutions, patients with commitments to an institution, or a patient who is detained or committed to an institution by a law court or by legal authorities.
25. **For Italy only:** Vaccination with a live attenuated vaccine within 6 weeks prior to randomization until the safety follow-up visit (see [Appendix 2](#) for all country-specific differences)

4.1.2. Part B: Open-Label Extension

4.1.2.1. Inclusion Criteria

1. Patient completed 48 weeks of treatment during Part A.
2. Patient will sign and date an ICF.
3. Patient is willing and able to comply with scheduled visits, treatment plan, study restrictions, laboratory tests, contraceptive guidelines, and other study procedures.
4. Patient agrees to the following methods of contraception:
 - Female patients of childbearing potential agree to continue using a highly effective method for avoidance of pregnancy for the duration of dosing and until 90 days after the last dose. For details regarding contraception requirements, refer to [Section 5.5.1](#).
 - Male patients must agree to use one of the contraception methods listed in [Section 5.5.1](#). This criterion must be followed from the time of the first dose of study medication and until 90 days after the last dose of study drug.

4.1.2.2. Exclusion Criteria

1. Any clinical condition that, in the opinion of the Investigator, might confound the results of the study or pose an additional risk in administering study drug to the patient.
2. Male patients with a female partner who is planning to become pregnant during the study or within 90 days after the last study drug dose.
3. Anticipated inability to comply with any study procedures, including participation in study visits.

4.2. RESCREENING OF STUDY PARTICIPANTS

Participants who are not enrolled within the screening period will be considered screen failures. Rescreening of participants for Part A is permitted with approval of the Medical Monitor. Participants can only be rescreened once and must be reconsented at the time of rescreening. Rescreened participants will be assigned the same screening number assigned at initial screening.

Rescreening of participants is not permitted if the reason for screen failure includes any of the following:

- Did not have a Clinical Severity Score of 2 to 4 (Ricci score; range 0 to 5) at screening (failure to meet inclusion criterion 3)
- Did not have a screening total RSA (Q1-Q4) without weight in the dominant UE assessed by RWS ≥ 0.2 and ≤ 0.7 (failure to meet inclusion criterion 4)
- Meets any of the exclusion criteria

Participants who are rescreened may not be required to repeat the MRI imaging if performed less than 60 days prior to study treatment administration.

Rescreening is not applicable for the Open-Label Extension (Part B).

4.3. WITHDRAWAL OF PATIENTS FROM STUDY TREATMENT AND/OR THE STUDY

4.3.1. Reasons for Withdrawal/Discontinuation

Patients may withdraw from the study at any time and for any reason without prejudice to their future medical care by the Investigator or at the study site. Every effort should be made to keep patients in the study, including if a patient decides to prematurely discontinue study treatment (see [Section 4.3.2](#)). The reasons for a patient not completing the study will be recorded. A patient may be withdrawn from the study drug for any of the following reasons:

1. The patient does not meet the protocol inclusion or exclusion criteria.
2. The patient is noncompliant with the protocol.
3. The patient has laboratory safety results that reveal clinically significant hematological or biochemical changes from the baseline values.
4. The patient has symptoms or an intercurrent illness not consistent with the protocol requirements or that justify withdrawal.
5. The patient is lost to follow-up.
6. Other reasons (eg, development of contraindications of use of study drug).

A patient must be withdrawn from the study drug for any of the following reasons:

1. The patient has a serious or intolerable AE(s) that, in the Investigator's opinion, requires withdrawal from the study.
2. The patient withdraws consent, or the Investigator or Sponsor decides to discontinue the patient's participation in the study.
3. The patient becomes pregnant.

The Investigator will also withdraw a patient if Fulcrum terminates the study. Upon occurrence of a serious or intolerable AE, the Investigator will confer with the Sponsor. If a patient is

discontinued because of an AE, the event must continue to be followed to satisfactory resolution as described in [Section 7.4](#). Any patient may withdraw his or her consent at any time.

4.3.2. Handling of Withdrawals

Patients are free to withdraw from the study or study treatment at any time upon request. Patient participation in the study may be stopped at any time at the discretion of the Investigator or at the request of the Sponsor.

Patients who discontinue study treatment or active participation in the study will no longer receive study drug. When a patient withdraws from the study treatment or active participation in the study, the reason(s) for withdrawal shall be recorded by the Investigator on the relevant page of the electronic case report form (eCRF).

If a patient prematurely discontinues study treatment, they will be encouraged to remain in the study and continue with all other aspects of the study. If appropriate, patients can restart study drug at the Investigator's discretion (depending on the reason for discontinuation of study treatment), after approval from the Sponsor.

If a patient decides to prematurely discontinue study treatment and not continue with all other aspects of the study, they will be considered to have withdrawn from the study. If a patient withdraws from the study, they will be asked to complete the early termination (ET) visit as soon as possible after the decision to terminate study participation and to complete the safety follow-up visit [REDACTED] days and a safety phone screen [REDACTED] days after their last dose of study drug. If the ET visit will be scheduled more than 7 days after the last dose of study drug, the safety follow-up and ET visits may be combined, with no duplication of assessments required.

Patients who fail to return for final assessments will be contacted by the site in an attempt to have them comply with the protocol. In the case of patients being lost to follow-up, at least 3 documented attempts to contact the patient must be made.

It is vital to obtain follow-up data on any patient withdrawn because of an AE or SAE. In every case, efforts must be made to undertake protocol-specified safety follow-up procedures.

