5. STUDY TREATMENTS

5.1. PART A: PLACEBO-CONTROLLED TREATMENT PERIOD

5.1.1. Method of Assigning Participants to Treatment Groups

Patients will be randomly assigned at the baseline visit (Day 1) to receive losmapimod (active drug) or placebo using a 1:1 allocation ratio. Randomization will be stratified to ensure that treatment allocation is balanced across FSHD repeat number categories (ie, 1 to 3 repeats versus 4 to 9 repeats) and by FSHD Type (FSHD1 versus FSHD2).

An Interactive Response Technology (IRT) system will be used to administer the randomization schedule. A designated unblinded statistician separate from the study team will generate the randomization schedule using the latest version of SAS software (SAS Institute, Cary, NC) for IRT, which will link sequential patient randomization numbers to treatment codes. The randomization will use an appropriate block size, which will not be revealed.

Patients can be randomized only once.

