9.1.1. Estimands and Intercurrent Events

The estimand of the primary analysis is the mean difference of the change from baseline in average total RSA Q1-Q5 with 500 g wrist weight at Week 48 between treatment groups in the full analysis set (FAS) (as per the ICH E9 (R1)). The FAS will consist of all patients with FSHD1 and FSHD2 who are randomized and receive at least one dose of study drug in the placebo-controlled treatment period. All observed data will be included in the primary analysis, including data collected after intercurrent events (as described in ICH E9 (R1) Addendum 2017), i.e., treatment discontinuation or a change in concomitant use of FSHD symptomatic medication. The change from baseline in average total RSA Q1-Q5 with 500 g wrist weight will be summarized by treatment group at each post-baseline visit. A mixed-effects model for repeated measures (MMRM) will be used as the primary analysis to analyze change from baseline in average total RSA Q1-Q5 with 500 g wrist weight, with terms for treatment group, visit, treatment group by visit interaction, baseline value, baseline value by visit interaction, region, and FSHD repeat number category, where appropriate. An unstructured covariance matrix will be used to model the correlations between repeated measurements within each patient. If the unstructured covariance matrix results in a lack of convergence, the first-order autoregressive covariance structure followed by the compound symmetric covariance structure will be used. The Kenward-Roger approximation will be used to estimate the denominator degrees of freedom. In the primary analysis, missing data are assumed to be missing at random ([Rubin 1976](#)).

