9.1.3. Sample Size Determination

The target population for this clinical trial is patients with FSHD1 and FSHD2. The clinical trial will reflect the current epidemiologic information about FSHD, with patients with FSHD1 making up approximately 95% of the study population and the other 5% being people living with FSHD2. However, all studies thus far have been conducted with FSHD1 patients; therefore, this calculation was based on that population. Additional FSHD2 patients will be enrolled to explore safety and efficacy in this subgroup.

Assuming the within-group SD of change is 0.08 and that 10% of the study population has missing Week 48 data, a sample size of 210 patients with FSHD1 (105 patients per group) will be needed to provide at least 95% power with a 2-sided test at 0.05 significance level to detect a difference of 0.05 between losmapimod and placebo in change from baseline in average total RSA Q1-Q5 with 500 g wrist weight at Week 48. An additional approximately 20 patients with FSHD2 will be recruited. The primary analysis will include patients with FSHD1 and FSHD2.

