9. DATA HANDLING CONVENTIONS

9.1 PREMATURE WITHDRAWAL AND MISSING DATA

Patients who prematurely discontinue study treatment will be encouraged to remain in the study and continue with all other aspects of the study. Patients who decide to discontinue study treatment

prematurely and not continue with all other aspects of the study will be considered to have withdrawn from the study.

The primary analysis of the primary endpoint will use a mixed-effects model based on restricted maximum likelihood estimation. The assumption will be made that, conditional on fixed and random effects, data are missing at random; therefore no imputation of missing data will be performed. The robustness of the analysis will be evaluated by sensitivity analyses with missing post-baseline values imputed using several imputation algorithms (see 10.2.1.2).

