A binary analysis may be carried out should meaningful score differences (MSDs) be determinable. An MSD is a measure of clinically meaningful within-patient change, which will be explored for change from baseline at 48 weeks in average total RSA Q1-Q5 with 500 g wrist weight, following the draft FDA guidance [6]. This exploration will be conducted by the sponsor's designated vendor. If the MSDs can be determined, for each treatment group, the number and percentage of patients at or above an MSD and the number and percentage of patients below the MSD will be presented. A patient with a missing change from baseline in average total RSA Q1-Q5 with 500 g wrist weight will be considered as below the MSD. The proportion of patients at or above MSDs at Week 48 will be compared between treatment groups using the Cochran-Mantel-Haenszel test stratified by FSHD repeat number category, and a two-sided p-value will be presented. Similar analysis will be performed using the lower bounds of MSDs as cut-off points as well as 0 as a cut-off point.

In addition, the analysis described in 10.2.1.1 will be repeated for the following:

- (1) Sensitivity analyses (see below)
- (2) For certain subgroups (listed in Section 8.5)

Sensitivity Analysis 1: MMRM with on-treatment measurements only

This sensitivity analysis of the primary endpoint will be similar to that used for the primary analysis of the primary endpoint. The key difference is that, for patients who prematurely discontinue study treatment, this MMRM will include only the measurements up to 2 days (inclusive) after the last dose of study drug.

Sensitivity Analyses 2, 3 and 4: MMRM with missing data imputed

In the primary analysis of the primary endpoint, missing data are assumed to be missing at random. To minimize the amount of missing data, patients who prematurely discontinue study treatment will be encouraged to remain in the study and continue with all remaining scheduled study visits for efficacy assessments.

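### The plan offers no partial follow-up to a patient who stops study drug, so Week 48 reachable-workspace values that the primary estimand uses may go uncollected

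*Protocol*

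**What the plan says.** Protocol 4.3.2 encourages a patient who stops study drug to stay for the rest of the study. If instead the patient stops drug and decides to "not continue with all other aspects of the study, they will be considered to have withdrawn from the study", that is the end of study participation. Table 7 footnote a and SAP Appendix B footnote a carry the same rule. SAP 9.1 says that those who stop early and choose to "not continue with all other aspects of the study will be considered to have withdrawn from the study". Neither document describes anything in between, such as attending Week 48 only.

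A withdrawn patient is asked for a prompt early termination (ET) visit, a safety follow-up visit and a safety phone call. No Week 48 visit is named. Under Table 7 footnote r, RWS is done at the ET visit only if at least 12 weeks have passed since the last visit.

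On the analysis side, Protocol 9.1.1 states: "All observed data will be included in the primary analysis, including data collected after intercurrent events". Treatment discontinuation is named as one of those events, and SAP 2.2.1 repeats this. SAP 10.2.1.2 adds that, to limit missing data, patients who stop drug will be encouraged to "continue with all remaining scheduled study visits for efficacy assessments".

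**The concern.** The estimand follows a treatment-policy strategy in substance: it wants the Week 48 value whether or not the patient is still on drug. The withdrawal rule gives sites two boxes, everything or nothing. Consider a patient who has stopped drug, is tired of MRI scans, blood draws or frequent travel, but would come once more at Week 48. As written, a site can class that patient as withdrawn, schedule an ET visit and ask for nothing further.

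The values at risk are off-drug values. If they are missing, the primary MMRM fills the gap implicitly from the observed patients in the same arm, most of whom are likely still to be taking drug. For losmapimod patients who have lost benefit, this moves the estimate above the effect that the plan defines.

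**Working it through.** **1. The plan's own power figure.** Inputs from Protocol 9.1.3: "Assuming the within-group SD of change is 0.08 and that 10% of the study population has missing Week 48 data"; 105 FSHD1 patients per group; "at least 95% power with a 2-sided test at 0.05 significance level to detect a difference of 0.05". Protocol 5.1.1 allocates patients "using a 1:1 allocation ratio".
- Patients with Week 48 data: 105 × 0.90 = 94.5 per arm.
- SE of the difference: 0.08 × √(2/94.5) = 0.0116.
- Two-sided power from the noncentral t distribution: 0.990. The stated lower bound is met.
- With 15%, 20% and 30% missing, power is 0.986, 0.981 and 0.964. Power is not the issue.

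**2. Does the ET visit supply the missing value?** Table 7 places visits at Days 1, 28, 84, 168, 252 and 336, so the gaps are 27, 56, 84, 84 and 84 days. The longest is 84 days, or 12 weeks. A patient who attended the last scheduled visit and then comes promptly for ET will usually be inside 12 weeks, so RWS is not required. If RWS is done, SAP 9.5.1 assigns it by study day. It counts as Week 48 only from Day 295 to Day 357 (or the first open-label dose, if earlier).

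**3. Do the sensitivity analyses cover the gap?** Under SAP 10.2.1.2 the three multiple-imputation analyses run only if 10% or more of patients in either arm lack the Week 48 change. A patient who leaves because of visit burden would fall under other reasons (missing category 2), unless an adverse event, noncompliance, investigator discretion or a prohibited medication is recorded. I read the category 2 text in Sensitivity Analyses 2 and 3, and the base imputation in Analysis 4, as drawing from the patient's own arm's mean. The 25th-percentile and placebo-based imputations apply only to category 1, and the tipping-point delta only to category 1 losmapimod patients. Loss of benefit in a category 2 patient is therefore not tested.

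**4. Possible size.** Take the plan's effect of 0.05. Assume that a share d of the losmapimod arm has stopped drug, is unseen at Week 48, and would by then look like placebo. The documents give no value for d.
- Treatment-policy value: 0.05 × (1 − d).
- Estimate if these patients are represented by the rest of their arm: about 0.05.
- Overstatement: 0.05 × d.

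| d | Treatment-policy value | Overstatement |
|---|---|---|
| 2% | 0.049 | 0.001 |
| 5% | 0.0475 | 0.0025 |
| 10% | 0.045 | 0.005 |
| 15% | 0.0425 | 0.0075 |

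If the unseen patients keep half the benefit, the overstatement halves: 0.0025 at d = 10%.

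**5. What a fix could recover.** Let a share r of these patients accept a Week 48 visit. The observed difference is then about 0.05 × (1 − d)/(1 − d + r × d). At d = 10%:
- r = 30%: 0.045/0.93 = 0.0484, so about 0.0016 is recovered.
- r = 50%: 0.045/0.95 = 0.0474, so about 0.0026 is recovered.

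With 115 per arm and 10% missing, the SE is 0.08 × √(2/103.5) = 0.0111, so the recovered part is about 0.14 to 0.24 SE. The values of r are assumptions. These are comparisons of observed means; the MMRM also uses each patient's earlier visits, so they are only a guide.

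**The case against.** The strongest reply is that the sentence is ambiguous. Not continuing with all other aspects can mean continuing with none of them, and Protocol 4.3.2 goes on to speak of a decision to end participation. Protocol 4.3.1 asks sites to make every effort to keep patients in the study, including those who stop drug. SAP 10.2.1.2 foresees intermittent missing values, and completers who lack the last visits, so partial attendance is not always withdrawal. This stands as a reading. But the text supports the other reading too, sites may differ, and nothing tells a site to ask for Week 48 alone.

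A reader might infer that the patient drops out of the primary analysis, or that data are thrown away. The documents do not support that. Membership of the full analysis set needs only randomization and one dose (Protocol 9.1.4, SAP 6.1), and every RWS value already recorded enters the model. Nor is a later assessment forbidden: SAP 9.5.1 would place an unscheduled value from Days 295 to 357 in the Week 48 window. The loss is of values never collected.

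It is also fair that the imputation analyses exist and would be triggered at 10% missing in either arm. Their coverage of this type of patient is limited, as shown above.

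**Conclusion.** The point holds as a gap in the follow-up wording. An all-or-nothing rule, with an ET visit that often omits RWS, can leave Week 48 values uncollected from patients willing to give them. The treatment-policy estimand then rests on missing at random for those patients.

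The size is unknown from the documents. Under full loss of benefit the overstatement is at most about 0.05 × d, and less if some benefit is kept. A reader might take the 10% row, where 0.005 is 11% of 0.045, as the bias caused by this rule. That is not supported: the plan's 10% is missing Week 48 data from all causes, and patients lost to follow-up or refusing everything cannot be recovered by rewording. Only the part from patients who accept partial follow-up is attributable to the rule. Power is not a reason to act. This is a cheap improvement and does not invalidate the primary analysis.

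**What to change.** In Protocol 4.3.2, Table 7 footnote a, SAP 9.1 and SAP Appendix B footnote a, add wording to this effect: a patient who stops study drug and declines some procedures or visits, but has not refused all further assessment, remains in the study and is asked to attend at least the Week 48 efficacy assessments within the Week 48 window. These are RWS, dynamometry, PGIC and Neuro-QoL UE, plus MRI if the patient is willing. Other visits follow as the patient is willing. The full schedule stays the first request. MRI belongs on the list because MFI in B muscles is in the first step after the primary test in SAP 2.4.2.

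Leave unchanged the provisions on discontinuation by the Investigator or Sponsor (4.3.1, 4.3.2), pregnancy (7.8.3) and unblinding (7.8.5). Withdrawal should not be redefined as consent withdrawal or loss to follow-up only, because that would contradict those sections.

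The cost is amendment wording. The Week 48 visit already exists, and the values enter the MMRM through the existing windows without a change to the analysis. The downside is that some patients may choose the reduced schedule over the full one, with loss of interim RWS or MRI data.
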